### **3.2.4 Compensation**

Each family will be given a total of \$50 incentive payments, a \$20 gift card at the first visit (includes initial measures and hair sample collection) and a \$30 gift card at the follow up visit (also includes measures and hair sample collection).

## **3.3 Interventions**

This is a one-group feasibility study. There is only one intervention group. The Overall-Study PI and Local PI will recruit professional Reiki practitioners who are trained at Level 3 or Master Level and have prior experience working with families and children. A Reiki Master will perform the initial teaching and instruct the parent how to perform a simple 15-minute Reiki session. Parents will complete a return demonstration using light touch with their adolescent. The parent will receive an introductory book on Reiki, an informational article, and a poster showing hand positions for their reference as well as the intervention log to record sessions. The initial teaching session will take about 1.5 hours with breaks. The initial teaching session will be conducted by a Reiki Master and will mark the beginning of Week 1. A Reiki practitioner (Master or Level 3) will provide a shorter "booster" session the following week to review techniques with the parent and answer questions. This session will last 45 minutes with breaks. The "booster" session will count as one day for that week. Parents will be asked

to complete a minimum of 15 minutes of Reiki with their adolescent at least five days per week for the four-week intervention period. Parents will receive a phone call from the research coordinator once per week during weeks three and four to check in with them and ask if they have any questions or problems with the intervention and will refer to a Reiki practitioner if needed.

## 4 Statistics and Data Handling

### 4.1 Statistical considerations

Primary outcomes (Aims 1): Feasibility will be examined by computing the proportion of approached subjects enrolled in the study, the proportion of subjects who complete Reiki training, and the proportion of enrolled subjects' who completed data collection. Qualitative data will be analyzed using a basic qualitative descriptive approach. Qualitative data (audio recorded interviews and field notes) will be transcribed verbatim, checked for accuracy, imported into Atlas.TI for data management, and analyzed. Portions of text are labeled or coded with terms that are descriptive of the user opinions and observations. Codes will be identified and defined in an iterative process by investigators independently coding the data and arriving at agreement in discussion/review. Codes are sorted and categorized into themes, which will be discussed in research meetings. We will use mixed methods to triangulate the qualitative and quantitative data to produce a more accurate picture of parental beliefs and experiences. These results will be used to refine procedures for future, larger studies. Qualitative results will be triangulated with quantitative results to answer questions of feasibility. Qualitative results will also be examined to explore the parents' confidence in delivering Reiki and beliefs in their ability to help their adolescent (Aim 3).

Secondary outcomes (Aim 2): Descriptive statistics will be used to check data distribution, identify outliers, examine the balance in baseline measurements, and report outcome measures (e.g. pain) at each time point. Trend plot will be used to visualize the trend of change over time. Pair-wise comparisons will be conducted to test the difference in the change in outcome measures (T0 versus T1, T1 versus T2, T0 versus T2) using two sample t-tests. We will not adjust for multiple comparisons to avoid further reduction of power. Mixed effect modeling for repeated measures will be used to examine the trajectories of treatment effect over time, adjusting for within-patient clustering from repeated measures and possible confounders.

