## 3 Study Design

This study is a mixed methods quasi-experimental one group design.

Parents of hospitalized ill children have been successfully taught to do Reiki with their children.

However, no study that we are aware of has taught parents of community-dwelling children or adolescents receiving palliative care, nor has any study taught parents of these adolescents in a prospective, scientific manner. As such, a one-group feasibility, acceptability study design is appropriate to examine teaching parents Reiki one-on-one in the home using a short teaching period and booster session. The design and sample size will achieve the goals of the study, including preliminary symptom outcome measures and parental feelings about learning Reiki and providing this intervention to their adolescents.

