### **3.2.1 Study events description**

Dyads will be in the study for a total of nine weeks from enrollment to the follow-up visit. Screening occurs at least weekly and prior to enrollment. Enrollment and initial study measure completion, including first hair sample collection from both parent and adolescent, will occur at the beginning of Week 0. Parents will fill out the Medication Log during Week 0 in order to have a baseline of pain and anxiety medications before study intervention begins. The parent will receive Reiki training, a poster with suggested hand positions and a commercially-available book about Reiki in the home on the first day of Week 1. A visit window is defined as a week (7days) -1/+3 days from the initial Reiki training. During Week 2 the parent will receive a Reiki booster session with a repeat of the training and may ask questions. The parent will administer at least 5 times per week for at least 10 minutes each session. During weeks 1-4, the parent will collect saliva samples for themselves and their adolescent before and after any two Reiki sessions as long as they are collected on two separate days. At the end of Week 4, measures will be repeated either in person or by phone. During Week 8, measures will be repeated, the second hair sample obtained from both parent and adolescent, and the parent will participate in a qualitative interview. The qualitative interview will be administered in person by trained OSU College of Nursing

study staff as part of the interview session. Interviews will be audio recorded using a hand-held audio recording device. Audio recordings will be transcribed verbatim. Audio recording is voluntary and participants can choose to not have their interview recorded and still be a part of the study. See Appendix 2 for schema.

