#### 4.1.1 Sample size

We will enroll 12 adolescent-parent dyads in order to achieve study objectives. The emphasis is on Aims 1 and 3, the feasibility and acceptability of the study as well as the parents' feelings about learning Reiki and their ability to help their adolescents. These aims will inform future study protocols. Aim 2 is exploring both parent and adolescent stress, symptoms, and overall quality of life. We are also testing data collection of hair and saliva in this population of adolescents receiving palliative care in the home. The preliminary results from the primary and secondary outcomes will inform the sample size of the next planned study, a two-group randomized controlled trial.

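### Aim 2 time-point comparisons are specified as two sample t-tests, although one group of 12 dyads is measured repeatedly and no paired test is named.

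*Combined protocol and SAP*

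**What the plan says.** All of this is in the combined protocol and SAP.

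- **The test.** Section 4.1, under the Aim 2 secondary outcomes, plans to "test the difference in the change in outcome measures (T0 versus T1, T1 versus T2, T0 versus T2) using two sample t-tests". It declines multiplicity adjustment so as not to lose more power.
- **The design.** Section 3 states: "This study is a mixed methods quasi-experimental one group design". Section 3.3 adds: "There is only one intervention group". Section 4.1.1 gives the size: "We will enroll 12 adolescent-parent dyads in order to achieve study objectives".
- **Repeated measurement.** After enrollment (T0), section 3.2.1 says: "At the end of Week 4, measures will be repeated either in person or by phone". It continues: "During Week 8, measures will be repeated, the second hair sample obtained from both parent and adolescent". These are T1 and T2.
- **The other Aim 2 analysis.** The same paragraph of section 4.1 plans a mixed model for trajectories over time, "adjusting for within-patient clustering from repeated measures and possible confounders".
- **Status of Aim 2.** Section 4.1.1 puts the emphasis on Aims 1 and 3 and states: "Aim 2 is exploring both parent and adolescent stress, symptoms, and overall quality of life".

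No section names a paired test or a second group.

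**The concern.** A two sample t-test takes its standard error from two independent samples. Every listed contrast here is within person, so the test leaves out the covariance between a person's own measurements and its standard error is wrong. The mixed model planned in the same paragraph accounts for that covariance, so the two analyses could give different p-values for the same contrast.

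The sentence is also ambiguous. It speaks of a difference in change, but its bracketed list pairs single time points. The error runs in opposite directions under the two interpretations.

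At stake are the p-values and confidence intervals for changes in symptoms and stress. On the levels reading the plan also works against itself: it forgoes multiplicity adjustment to protect power, then names a test that gives power away once the within-person correlation is moderate.

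**Working it through.** **Inputs from the documents:** one group (sections 3 and 3.3); n = 12 dyads (section 4.1.1); measurements at T0, T1 and T2 (Table 1, section 3.2.1). The plan has no power figure to reproduce.

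**Assumptions, because the documents give no significance level, SD, effect size, correlation or dropout:** two-sided 0.05; complete pairs; normal outcomes with equal SD σ at each time; within-person correlation ρ varied; change d in SD units.

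**Reading 1: levels at two times compared as independent samples**

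1. The two sample test assumes Var(mean difference) = 2σ²/n. The true variance is 2σ²(1 − ρ)/n. The standard error is therefore overstated by 1/√(1 − ρ): 1.20, 1.41 and 1.83 at ρ = 0.3, 0.5 and 0.7.
2. The 95% half-width of the two sample interval is t(0.975, 22) × √(2/12) = 2.074 × 0.408 = 0.85 SD at every ρ.
3. The paired half-width is t(0.975, 11) × √(2(1 − ρ)/12), with t = 2.201. The results are in the table.
4. The half-widths are equal when 1 − ρ = (2.074/2.201)², so ρ = 0.11. With 8 pairs the same formula gives 0.18.
5. Paired power is from the noncentral t with 11 df and noncentrality d√12/√(2(1 − ρ)). For d = 0.8 and ρ = 0.5 this is 0.8 × 3.464/1 = 2.77, giving 71%. Two sample figures are simulated.

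| ρ | Two sample type I error | Power, 0.5 SD: two sample v paired | Power, 0.8 SD: two sample v paired | Paired half-width (SD) |
|---|---|---|---|---|
| 0 | 5.0% | 22% v 20% | 47% v 43% | 0.90 |
| 0.3 | 2.2% | 18% v 27% | 46% v 57% | 0.75 |
| 0.5 | 0.9% | 15% v 35% | 46% v 71% | 0.64 |
| 0.7 | 0.2% | 11% v 53% | 46% v 90% | 0.49 |

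At ρ = 0.1 the two sample type I error is about 4.0%, and power for a 1.0 SD change is 66% v 65%, so pairing gains nothing there. With only 8 complete pairs, power for a 1.0 SD change is 46% v 54%, 68% and 88% at ρ = 0.3, 0.5 and 0.7.

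**Reading 2: T0-T1 change compared with T1-T2 change**

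1. Assume equal correlation ρ between all three times. Each change has variance 2σ²(1 − ρ). The changes share T1 with opposite signs, so their covariance is −σ²(1 − ρ) and their correlation is −0.5.
2. The true variance of the difference in mean change is (2 + 2 + 2)σ²(1 − ρ)/n = 6σ²(1 − ρ)/n. The two sample test assumes 4σ²(1 − ρ)/n, so its standard error is too small by √1.5 = 1.22.
3. Simulated rejection with no true change is about 11% at ρ = 0.3, 0.5 and 0.7. The paired test holds 5%.

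**The case against.** The strongest reply is that the plan already contains a valid analysis. The mixed model shows that the authors knew the data were correlated, and the t-test label, which sits beside a reference to pair-wise comparisons, may be loose wording. Aim 2 is exploratory, no success or stopping rule uses these p-values, and the size of the loss rests wholly on assumed correlations and effects.

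Most of that stands, and it limits the weight of the point. It does not make the named test right. Pair-wise refers to pairs of time points, and the mixed model is set out as a separate analysis of trajectories, not as the source of these contrasts. If a paired test was intended, the text should say so.

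Several stronger inferences are tempting, but the documents do not support them:

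- **That a test of changes is impossible with one group.** Three time points give two changes per person, so one can be run. It is still within person.
- **That the named test is simply conservative.** That holds on the levels reading only. On the change reading it rejects too often.
- **That the two sample interval is sound below a correlation of 0.11.** It over-covers at any positive correlation. The 0.11 marks only where the paired interval becomes the narrower one.
- **That the study will miss real changes.** The loss falls on one of two planned analyses.
- **That saliva sessions will be pooled as if independent.** No section proposes this. Saliva is collected around sessions in Weeks 1-4, not at T0, T1 and T2, so the quoted sentence does not cover it.

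**Conclusion.** The point holds, and the sentence should be corrected. The named test does not fit a one-group repeated-measures design and is invalid on both readings; the direction of the error depends on the reading. The bracketed list favors comparing levels. There the test is conservative, and the cost in power ranges from nothing at a correlation near 0.1 to a large loss at 0.7. The documents cannot say where this trial lies in that range. The 11% rejection rate on the other reading rests on equal correlations between time points.

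The effect stops at p-values and intervals from one of two planned analyses of an exploratory aim. The feasibility proportions and the qualitative results are untouched. With complete pairs, the estimated mean change is the same whichever test is used.

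**What to change.** In section 4.1, replace the two sample t-tests with paired t-tests on within-person change, or take the time contrasts from the planned mixed model. Report each mean change with its 95% CI, and run adolescents and parents separately. State plainly that each contrast compares the same person's measurements at two time points, which removes the ambiguity about change.

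List only the contrasts for which data exist under Table 1 and section 3.2. Hair cortisol has T0 versus T2 only. The medication log covers Weeks 0-4 and so has no T2 contrast.

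The cost is a wording change in section 4.1, with no extra data and no extra participants.

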#### 4.1.1 Sample size

We will enroll 12 adolescent-parent dyads in order to achieve study objectives. The emphasis is on Aims 1 and 3, the feasibility and acceptability of the study as well as the parents' feelings about learning Reiki and their ability to help their adolescents. These aims will inform future study protocols. Aim 2 is exploring both parent and adolescent stress, symptoms, and overall quality of life. We are also testing data collection of hair and saliva in this population of adolescents receiving palliative care in the home. The preliminary results from the primary and secondary outcomes will inform the sample size of the next planned study, a two-group randomized controlled trial.

## 4.2 Management of data

### 4.2.1 Source documents [Site data management]

Source documents are the original records of participant information. The ICH-GCP guidelines define source documents as "original documents, data, and records." Source documents may include study-specific Data Collection Tools (DCTs). DCTs are instruments/tools used to collect/document the requested data at each of the sites involved in the project. The DCTs contain those variables listed in this protocol. Examples of DCTs may include medication logs, Reiki log, research files, surveys and specific research worksheets used to

document key research data elements. Consent forms (if applicable) and an enrollment log are kept at the sites to know which participants are being followed and to ensure accurate enrollment and comply with local IRB regulations. Source documents/DCTs remain at the site of collection.

#### **4.2.2 Data capture [Data management]**

Study site personnel will complete screening, enrollment, and make sure initial measures are complete. Site personnel will scan and email completed paper forms to the Overall PI via secure email transmission for double data entry or will enter data collected via research electronic data capture (REDCap). Any paper/scanned data will be entered into SPSS by the PIs undergraduate students who have been trained in double data entry and data checking.

As part of the NIH data sharing directive, de-identified data from this study will be transferred to the PCRC Data Repository located at the University of Colorado.

#### **4.2.3 Record retention**

- Any study records (including DCTs, etc.) will be retained in the site's research record for 10 years after the study is completed in accordance with Good Clinical Practice guidelines. At that time the research information will be destroyed by each site's research document destruction rules/regulations.
- Any research information already included in medical records will be kept indefinitely.
- The de-identified data that are collected and entered will remain in the PCRC Data Repository indefinitely.

#### **4.2.4 Data sharing [REQUIRED LANGUAGE]**

De-identified study data from this study will be transferred to the PCRC Data Repository located at the University of Colorado. The PCRC fully supports the Final NIH Statement on Sharing Research Data and will provide assistance to all investigators and personnel for compliance. Consistent with OMB Circular A-110 and subsequent NIH Grants Policy Statements, the PCRC will provide access to all de-identified data collected as part of PCRC-supported investigations, insofar as access is consistent with IRB/CHR rules, local, state, and Federal laws and regulations, and the HIPAA Privacy Rule.

### **5 Ethics and Dissemination**

#### **5.1 Ethics and regulatory compliance**

We will submit this protocol and supporting documents (i.e., measures, consent) to the IRBs of Ohio State University (OSU) and Children's Hospital. OSU will cede control of the study to Children's Hospital IRB as the IRB of record per previous studies conducted at the same site with the same study team. We will seek additional language required by the PCRC for IRB applications and consent forms as well as advice from PCRC experts after funding.

#### **5.2 Confidentiality**

Every effort will be taken to ensure the confidentiality of study participants and their data. Only IRB-approved study team members who have completed human subjects research training will have access to study data. All study data, with the exception of consent forms, will be identified by a code number only. Consent forms and the list linking study participant names and code numbers will be kept in a locked drawer in a locked office separate from other study data. Participants will be referred to by code number only. All reasonable effort will be made to maintain participant confidentiality.

## 5.3 Data security

The Ohio State University (OSU) College of Nursing has secure electronic data servers that are password protected and behind firewalls. All electronic data will be stored on these secure servers. Additionally, data sent electronically will be identified by code number only. Paper data, including consent forms, will be stored onsite. Consent forms and the list linking names and code numbers will be stored separately from other data. Audio recordings from the interview will be recorded using hand-held audio recording devices and the files transferred to password protected computers at OSU. These audio files will be identified with a subject ID only. Files are saved on the OSU College of Nursing server, which is password protected, regularly backed up, and only accessible by authorized study team members. Once the files are saved onto the computer, the file will be deleted from the recording device. Files may be kept on the server for up to 5 years. Only study personnel will have access to either paper or electronic data.

# 6 Safety Considerations

## 6.1 Risks

The risk of participating in this study are minimal. Reiki is non-invasive and can therefore be used with anyone. NCCIH considers Reiki to be safe although little scientific evidence exists about its effectiveness. There is the possibility that either the parent or adolescent may become uncomfortable during the Reiki session. If this happens, they should either take a break or change positions to be more comfortable. There is a risk for becoming tired or having pain due to the adolescent's illness during the Reiki session. If either of these happens, the dyad should take a break and/or change positions to one that is more comfortable. Some of the data collection may be uncomfortable or inconvenient for the parent and/or adolescent. The hair sample collection may cause a slight physical discomfort due to the gentle pull on the hair before cutting and may cause social discomfort if the parent or adolescent feels as though the small bare spot on the scalp where the hair was clipped may show. Any study personnel who will be collecting hair will be trained to perform the sample cut gently and in a spot not likely to show. Collecting the saliva samples may be inconvenient for the parent as two samples must be collected (pre and post) for both the parent and adolescent (four samples total each time) twice per week for four weeks and stored in the home freezer. We will provide pre-labeled sample tubes and baggies so that the parent only has to add the date to each baggie in order to decrease the inconvenience as much as possible.

**Adverse Events.** All adverse events (AEs) and serious adverse events (SAEs) will be tracked, documented, and reviewed. In one systematic review evaluating the efficacy of Reiki, nine randomized control trials reported no adverse events. It is anticipated that AEs in this study will be minimal. However, for the purpose of this study, AEs will be defined as clinically significant mental status changes, or any other unusual symptom or event (e.g. significant pain, a fall) that occur during the time frame of each Reiki session. An SAE will be defined as any untoward medical occurrence that results in death, is life threatening, results in hospitalization, or results in persistent or significant disability. Parent participants will be instructed to call the research coordinator for the study to report any adverse or unusual events. Parents will be instructed to call 911 in the event of a medical emergency and report the emergency to the research coordinator or the palliative care on-call medical provider (physician or nurse practitioner) when they are able. In either case, the research coordinator will consult with one of the palliative care physicians or nurse practitioners immediately in the case of an SAE or within 24 hours of an AE. The PI of the study will be notified of all AEs and SAEs immediately via email for AEs and text message and email for SAEs. All AEs and SAEs will be reported to the IRB in a timely manner.

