salivary cortisol. A four-week follow-up period was chosen in order to obtain an accurate measure of HCC to determine any change in stress during the intervention period. Approximately 10-75 mg of hair is cut from the posterior vertex region of the scalp as close to the scalp as possible. The posterior vertex has the lowest variation in cortisol levels, and is the preferred area for sampling. Co-I ([name]) will train the PI and Co-I ([name]) on hair collection. We will take one cut at the first home visit (T0) and another at the four-week follow-up home visit (T2). Assay: Each 1 cm of hair approximates the mean cortisol level over the prior 1 month. Samples are assayed in duplicate and inter- and intra-assay coefficients of variation calculated. HCC levels are expressed in hair as pg/mg.

Saliva collection and assay: Salivary alpha amylase (sAA) is a non-invasive biomarker that detects immediate changes in autonomic nervous system response, signaling a change in level of stress. Interventional studies have shown a decrease in sAA levels as a response to an intervention meant to stimulate relaxation. Collection: The Salimetrics Drool Tube for adults will be used for saliva collection from the parents and cognitively aware adolescents. The SalivaBio Swab for infants will be used for the remaining adolescents to eliminate any choking hazards. Samples will be collected for both parent and adolescent pre and post two Reiki sessions per week for four weeks. Storage: The swab will be placed in a Swab Storage Tube. Tubes will be put into a sealable plastic bag marked as parent or adolescent, the date and time of collection, and put into the home freezer until the PI or other team member collects them at the follow up visit. Samples will be transported on dry ice to the lab, and frozen at -20C until processed. Assay: The saliva samples will be batch processed after thawing using the Salimetric Alpha Amylase assay following manufacturer's instructions. The amount of alpha-amylase activity present in the saliva sample is directly proportional to the increase in absorbance at 405 nm.

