Throughout the study the Overall study PI and Local PI will be responsible for monitoring participants for adverse events. The following will be considered SAEs: patient death, attempted suicide, major depression, or breach of confidentiality. The following will be considered AEs: patient allegations of physical/mental injury during the study, patient allegation of inappropriate consenting or recruitment procedures. The Overall study PI and Local PI will review AEs and unanticipated problems within 24 hours of notification of the event. Unanticipated problems that are SAEs will be reported within one week of the investigator becoming aware of the problem. Any other unanticipated problems should be reported within two weeks of the investigator becoming aware of the problem. All fatal or serious/life threatening AE will be reported to the IRB in accordance with IRB policy. Non-serious AEs will be reported to the IRB at time of continuing review. AEs determined as anticipated problems involving risks to subjects or others will be reported to IRB at time of continuing review. The Overall study PI and Local PI will be informed by team members about any AEs or unanticipated problems immediately. If protocol changes are needed, the research coordinator, with Overall study PI and Local PI approval, will submit a modification request to the IRB. Protocol changes will not be implemented prior to IRB approval unless necessary to eliminate apparent immediate hazards to the participants.

At each meeting of the SMC during the conduct of the trial, the SMC will make a recommendation to the Overall study PI to continue or to terminate the trial. This recommendation will be based on safety considerations. The Overall study PI is responsible with the SMC for safeguarding the interests of participants and for the conduct of the trial. The Overall study PI will be responsible for deciding whether to continue or to stop the trial based on the SMC recommendations.

- D. For multi-site studies, procedures to ensure compliance with the monitoring plan and reporting requirements across study sites.

This is a single site study.

- E. An assessment of external factors or relevant information (i.e., developments in the literature, results of related studies) that may have an impact of the safety of participants or on the ethics for the research study.

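### Section 6.1 counts non-serious adverse events only during Reiki sessions, and Section 6.3 C adds only alleged injuries, so some saliva, hair and post-session events meet neither definition

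*Combined protocol and SAP*

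**What the plan says.** The rules that bear on this point sit in several places.

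- **AE definition, Section 6.1.** An AE is a clinically significant change in mental status, "or any other unusual symptom or event (e.g. significant pain, a fall) that occur during the time frame of each Reiki session". The time frame of a session is not defined.
- **SAE definition, Section 6.1.** "An SAE will be defined as any untoward medical occurrence that results in death, is life threatening, results in hospitalization", or in lasting or significant disability. It carries no session limit.
- **Reporting instruction, Section 6.1.** "Parent participants will be instructed to call the research coordinator for the study to report any adverse or unusual events". This has no session limit either.
- **Second AE definition, Section 6.3 C.** "The following will be considered AEs: patient allegations of physical/mental injury during the study", together with allegations about consent or recruitment. Again there is no session limit, but an allegation is needed.
- **Saliva.** Sections 3.2, 3.2.1 and 3.2.2 have the parent collect samples from both members of the dyad before and after two sessions a week for four weeks. Parents and cognitively aware adolescents use a drool tube. For the others, "The SalivaBio Swab for infants will be used for the remaining adolescents to eliminate any choking hazards". Section 6.1 describes the same procedure this way: "Collecting the saliva samples may be inconvenient for the parent".
- **Hair.** Section 3.2 schedules one cut at T0 and one at T2. Section 6.1 does list a risk here: "The hair sample collection may cause a slight physical discomfort due to the gentle pull on the hair before cutting".
- **Purpose.** Section 4.1.1 says that collecting hair and saliva in this population is itself being tested, and that the results will inform a randomised trial.

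**The concern.** The Section 6.1 window is tied to the Reiki session, yet participants undergo two other physical procedures, hair cutting and saliva collection. Neither takes place during the session itself. One of them, saliva collection, is done by parents, and its device was chosen for some adolescents with choking in mind. Those adolescents are the ones least able to describe what happened to them.

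At stake is how a non-serious event is classified. A parent could telephone about a swab that made the adolescent gag. The coordinator, applying Section 6.1 as written, would have no AE category for it. An AE summary built on these definitions could then show none for the sampling procedures, and the later trial would be planned on that summary. A reaction that begins shortly after a session ends has the same problem.

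**Working it through.** The plan states no figure on this point. The check is a comparison of text, plus simple counts for scale.

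**Step 1: when each procedure happens.** Enrolment and the first hair cut come at the start of Week 0, and Reiki training opens Week 1 (Section 3.2.1). The intervention lasts four weeks (Section 3.3), and the second cut is in Week 8. No Reiki session is scheduled at either cut. Each saliva pair brackets a session, one sample before and one after.

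**Step 2: run typical events through each rule.**

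| Event | AE under 6.1 | AE under 6.3 C | SAE under 6.1 |
|---|---|---|---|
| Fall during a session | Yes | Only if alleged as injury | Only if serious |
| Non-serious reaction starting after a session ends | No, unless the time frame is stretched | Only if alleged as injury | No |
| Gagging on a swab before or after a session, resolves | No on a plain reading; yes if the time frame takes in the paired sampling | Only if alleged as injury | No |
| Minor scalp nick at T0 or T2 | No on any reading | Only if alleged as injury | No |
| Choking that is life threatening or leads to hospital admission | Not needed | Not needed | Yes, at any time |

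Rows two to four share a gap: a non-serious event that nobody alleges as an injury meets no definition.

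**Step 3: do other contacts close the gap?** Parents are told to report anything adverse or unusual, so the information may reach the team, but neither definition then tells the team to count it. The calls in weeks three and four ask about the intervention (Section 3.3). The intervention log has a column for reactions to the session. Neither prompts for saliva or hair events.

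**Step 4: scale, if all planned samples are taken in 12 dyads (Section 4.1.1).**

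- Adolescent saliva: 2 (before and after) × 2 sessions a week × 4 weeks = 16 each; 16 × 12 = 192. With parents: 2 × 192 = 384.
- Adolescent hair: 2 cuts × 12 = 24. With parents: 2 × 24 = 48.

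The 192 mixes swab and drool-tube collections. The documents do not say how many adolescents will use the swab, so that share could be anything from none to all.

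**Step 5: risk text side by side.** Sections 3.2 and 3.2.2 give choking as the reason for the swab. Section 6.1, on saliva, speaks only of inconvenience. Its general remark that some data collection may be uncomfortable names no physical hazard of saliva sampling.

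**The case against.** The strongest reply is that Section 6.1 is not the only safety rule. Section 6.3 C counts alleged injury at any time in the study, and a parent could make the allegation for the adolescent. SAEs have no window. Parents are asked to report widely, the Safety Monitoring Committee reviews any untoward events reported to it, and unanticipated problems have their own route to the IRB. Section 3.2 also says the interviews will seek parents' views of the study as a whole. All of this stands. A reader might infer that the trial has no means of reporting harm from saliva or hair collection; the documents do not support that. What they leave open is whether a reported non-serious event is classed and counted as an AE.

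Three further limits also stand.

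- Because the time frame is undefined, paired saliva sampling could be read as inside it. The 192 collections lie outside only on the plain reading. No such reading reaches hair cutting.
- Choking is named as a hazard the swab is meant to remove. A reader might infer that the protocol admits a remaining choking risk with the swab. It does not, and the documents give no evidence either way.
- Hair is cut by trained study personnel, who would see a scalp injury themselves. The concern about an unseen event applies to saliva, not hair; for hair the gap is only one of classification.

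Finally, this is a minimal-risk study of 12 dyads with no AE endpoint. That limits the weight of the point but does not remove it, since the sampling procedures are themselves under test.

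**Conclusion.** The point holds in a limited form. Sections 6.1 and 6.3 C define AEs differently, and between them they leave out non-serious events from study procedures, or after a session, that nobody alleges as an injury. The gap is certain for the 24 planned adolescent hair cuts (48 with parents). For the 192 planned adolescent saliva collections (384 samples with parents) it rests on the plain reading that before and after a session is not during it. These are counts of opportunities, assuming full enrolment and complete sampling; the documents give no rate of events. SAEs are not affected.

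Separately, Sections 3.2 and 3.2.2 name choking when explaining the choice of swab, and the saliva risk text in Section 6.1 does not mention it. The removed consent pages may cover it, so nothing is concluded about what participants are told.

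This is a cheap improvement to safety capture and does not call the design into question.

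**What to change.** 1. Reconcile Sections 6.1 and 6.3 C into one AE definition: an unusual symptom or event in the adolescent or parent that occurs during any study procedure (Reiki session, saliva collection, hair collection), or that the parent or staff link in time to one, within a stated window after it. The sponsor should set the length of that window for each procedure. It needs an end point: an open window from T0 to T2 would take in much of the illness course of a palliative population.
2. Keep alleged injury during the study as an added category if wanted, and align the two SAE lists at the same time, since they also differ.
3. Record which procedure each AE followed, and report AEs by procedure.
4. Reconcile the saliva risk text in Section 6.1 with the choking hazard named in Sections 3.2 and 3.2.2.

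The cost is a few sentences and one field on whatever form is used for AEs (none is shown in Appendix 3). The downside is small: some symptoms of the underlying illness will be recorded, which the bounded window and the required link to a procedure keep in check.
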